6.1.4 Model checking procedures

Assuming missing at random, a patient with missing value at a visit will still contribute to the estimation of the treatment effect at the particular visit as the likelihood-based repeated measures ANCOVA borrows information from non-missing values of this patient and other patients.

6.1.5 Sensitivity analysis

As a sensitivity analysis the Bayesian analysis in [Section 6.1.3](#) will be repeated with varying values of the effective sample size for the placebo prior. A further sensitivity analysis using different values of the common variance assumed in the likelihood function and the prior may be performed as needed. A Bayesian analysis without assuming the variance is known in the likelihood function may be performed as well.

If more than 10% of the data for the Bayesian analysis on the change from baseline to Week 12 in ALT are missing then as a sensitivity analysis the Last Observation Carried Forward (LOCF) approach and/or another method may be used to impute missing data and the Bayesian analysis re-conducted.

6.1.6 Supportive analysis

The subgroup of subjects in Cohort 2, meeting the Cohort 1 ALT inclusion criterion (ALT \geq 60 IU/L (males) or \geq 40 IU/L (females)), may also be analyzed separately, if enough subjects meet the criterion. The analyses may include, but not limited to, the same descriptive and inferential analyses described in [Sections 6.1.2](#) and [6.1.3](#) respectively. Additionally a repeated measures ANCOVA with 4 levels for the treatment effect (100 mg LMB, placebo to 100 mg LMB, 50 mg LMB, placebo to 50 mg LMB) may be performed to compare LMB to placebo within each cohort.

6.2 Secondary objectives

6.2.1 Variables

The secondary variables of this study are:

- Intrahepatic lipid: Percent (%) Liver fat as measured by Magnetic Resonance Imaging (MRI).
- Anthropometric assessments: Weight, BMI, waist-to-hip (WTH) ratio
- Non-invasive markers of liver fibrosis:
 - Fibroscan[®] (in a subset of patients)
 - Enhanced liver fibrosis panel (ELF) and fibrosis biomarker test (originally known as Fibrotest[®]/FibroSure[®]).
- Fasting lipid profile: total cholesterol, HDL, LDL and triglycerides
- Itch scored on 100 mm visual analog scale (VAS) ratings.

Baseline for all secondary parameters is defined as the last measurement prior to the first dose.

6.2.2 Descriptive analyses

The secondary variables and the corresponding change from baseline and percent change from baseline will be listed by treatment, subject and visit/time and descriptive statistics will be provided by treatment and visit/time, as needed. Summary statistics will include mean (arithmetic and geometric), SD, CV (arithmetic and geometric), median, minimum, maximum as appropriate.

Graphical methods will be employed to show group summary plots over time by treatment as required.

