6.2.3 Statistical model, assumptions and hypotheses

Log-transformed ratio to baseline % liver fat and fasting lipid profiles as well as change from baseline % liver fat, weight, BMI, WTH ratio and itch VAS score will be analyzed. Parameters with more than one post-treatment measurement will be subjected to the same repeated measures ANCOVA described for the primary analysis using log-transformed baseline in lieu of untransformed baseline as a covariate for the log-transformed data analysis. For parameters with only one post-treatment measurement an ANCOVA with treatment as a classification factor and baseline (or log-transformed baseline if applicable) as a covariate will be employed.

Fibroscan® (in a subset of patients), ELF and fibrosis biomarker test data will be analyzed similarly and the log-transformation applied prior to the analysis as needed. For % liver fat, if historical placebo control data in a similar patient population are identified in the literature or become available from in-house studies later on then they may be incorporated into a Bayesian analysis as described for ALT.

The subgroup of subjects with baseline liver fat $\geq 10\%$ may be analyzed separately as needed.

Corporate Confidential Information

7 Statistical methods for safety and tolerability data

All subjects within the Safety analysis set will be included in the safety data analysis.

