10.1.2 Fibrosis biomarker test, originally called Fibrotest®/ Fibrosure®

The score is calculated as:

$$z = 4.467 \times \log_{10}(\alpha 2\text{-macroglobulin}) - 1.357 \times \log_{10}(\text{Haptoglobin}) + 1.017 \times \log_{10}(\text{GGT}) + 0.0281 \times \text{Age} + 1.737 \times \log_{10}(\text{Bilirubin}) - 1.184 \times \text{ApoA1} + 0.301 \times \text{Sex} \text{ (0=female, 1=male)} - 5.540.$$

Where:

$\alpha 2$ -macroglobulin is given in g/L,

Haptoglobin is given in g/L,

GGT is given in U/L,

Age is given in years,

Bilirubin is given in $\mu\text{mol/L}$,

ApoA1 is given in g/L,

Sex is given as 0 for female and 1 for male.

Reference: [<http://www.google.com/patents/US6631330>]

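### Percent change from baseline has the wrong sign for the fibrosis biomarker score whenever the baseline score is negative, because the SAP defines that score as an unbounded z

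*SAP*

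**What the plan says.** SAP 6.2.1 includes among the secondary variables the "Enhanced liver fibrosis panel (ELF) and fibrosis biomarker test (originally known as Fibrotest" entry, so the rules for secondary variables apply to it. SAP 10.1.2 introduces its formula with "The score is calculated as" and gives z, a weighted sum of log10 alpha2-macroglobulin, log10 haptoglobin, log10 GGT, age, log10 bilirubin, ApoA1 and sex, minus 5.540. Nothing after the formula maps z to a bounded scale, and nothing says that a laboratory-reported score will be used instead.

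SAP 6.2.2 then sets the descriptive outputs: "The secondary variables and the corresponding change from baseline and percent change from baseline will be listed by treatment, subject and visit/time". It makes no exception for a score that can be zero or negative. The same sentence goes on to provide descriptive statistics where needed, and the next one reads "Summary statistics will include mean (arithmetic and geometric), SD, CV (arithmetic and geometric), median, minimum, maximum as appropriate".

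For inference, SAP 6.2.3 says "ELF and fibrosis biomarker test data will be analyzed similarly and the log-transformation applied prior to the analysis as needed", and where data are log-transformed the baseline covariate is logged too.

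**The concern.** Percent change, ratio to baseline, logarithms and geometric means suit quantities that are always positive. z is not one. With a negative denominator, a rise in the score is listed as a negative percentage and a fall as a positive one. Patients with positive baselines in the same listing keep the correct sign, so a reader cannot repair the column by flipping it. Any summary of that column would mix the two groups. The test serves the secondary objective on non-invasive fibrosis markers, and two columns that should agree in direction would disagree for part of the trial population.

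Itch VAS has a related problem. Protocol 8.5.6 anchors 0 at no itch, and percent change from a baseline of 0 is undefined. Those are the patients in whom new itch would show.

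**Working it through.** The documents state no numerical result for this score, so there is no plan figure to reproduce. The check applies the SAP formula directly.

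**Inputs from the SAP (10.1.2).** z = 4.467 log10(alpha2-macroglobulin, g/L) - 1.357 log10(haptoglobin, g/L) + 1.017 log10(GGT, U/L) + 0.0281 age + 1.737 log10(bilirubin, µmol/L) - 1.184 ApoA1 (g/L) + 0.301 sex (male = 1) - 5.540.

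**Assumed inputs.** All patient values below are assumptions. Percent change is taken in its usual form, 100 × (post - base)/base, which the SAP does not spell out.

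**Algebra.** If base < 0, dividing (post - base) by base reverses its sign. This needs no assumption about patients or about which direction is clinically worse.

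**Patient A**: male, 52 years, alpha2-macroglobulin 2.0, haptoglobin 1.2, GGT 60, bilirubin 10, ApoA1 1.4.
- Baseline z = 1.345 - 0.107 + 1.808 + 1.461 + 1.737 - 1.658 + 0.301 - 5.540 = -0.653.
- With alpha2-macroglobulin at 2.3, the first term becomes 1.616 and z = -0.382.
- Change = +0.271. Percent change = 100 × 0.271/(-0.653) = -42%.

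**Patient B**: female, 45 years, values in the same order 1.6, 1.4, 40, 8, 1.5.
- z = -2.140. With alpha2-macroglobulin at 1.9, z = -1.807.
- Change = +0.333. Percent change = -16%.

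**Patient D**: male, 62 years, values 3.0, 0.8, 100, 12, 1.3.
- z = +1.135, so any percent change has the right sign.

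**Near zero.** A move from -0.3 to +0.2 is a change of +0.50, a percent change of 100 × 0.5/(-0.3) = -167%, and a ratio of -0.67, which has no logarithm. A move from -0.05 to +0.2 gives -500%.

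**How often baseline z is negative.** Four populations were simulated with lognormal analytes, normally distributed age and ApoA1, and equal sexes. The table gives assumed medians (means for age and ApoA1).

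| Scenario | alpha2-M | Haptoglobin | GGT | Age | Bilirubin | ApoA1 | z < 0 |
|---|---|---|---|---|---|---|---|
| Low | 1.6 | 1.3 | 45 | 50 | 9 | 1.45 | 97% |
| Central | 1.9 | 1.2 | 55 | 53 | 10 | 1.38 | 83% |
| High | 2.2 | 1.1 | 65 | 56 | 11 | 1.32 | 61% |
| Very high | 2.6 | 0.9 | 80 | 60 | 12 | 1.25 | 28% |

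A wide uniform box (alpha2-macroglobulin 1 to 3.5, haptoglobin 0.3 to 2.5, GGT 15 to 200, age 18 to 75, bilirubin 4 to 20, ApoA1 1.0 to 1.9) gives 73%, with z from -4.8 to +3.0.

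**Instability.** With an assumed within-patient SD of change of 0.2 to 0.6 and no treatment effect, 9% to 25% of patients in the central scenario have an absolute percent change above 100%.

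**Log option.** log z and log baseline do not exist for z ≤ 0, so a log analysis would lose the shares in the last column of the table. Geometric means and CVs of z fail for the same reason.

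**The case against.** The strongest reply is that the damage is confined to one column. SAP 6.2.2 lists the variable and its absolute change beside the percent change, so the correct direction is visible for every patient. Only the listing is unconditional: group descriptive statistics, geometric statistics and the log step are all left to judgement. An ANCOVA on absolute change with untransformed baseline is already open under SAP 6.2.3. The study is non-confirmatory, and SAP section 2 names Fibroscan and the ELF panel, but not this test, among the key secondary parameters for first interpretable results. All of that stands, and it limits the point.

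A reader might infer that a log-ratio analysis would silently reverse the treatment comparison, since the ratio of two negative scores is positive and its log runs the wrong way. The plan does not support this. SAP 6.2.3 also requires a logged baseline covariate, so every patient with baseline z ≤ 0 would drop out of the model. That would be a conspicuous failure and is unlikely to pass as a result.

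Discretion does not remove the core problem. The percent-change listing is not discretionary on its plain wording, and for the optional steps the SAP gives the programmer no rule that z can be negative.

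For itch VAS, SAP 6.2.3 already analyses change from baseline, so only the descriptive percent-change and geometric summaries are at issue.

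**Conclusion.** The point holds for the percent-change column. As written, the SAP produces a percent change with the wrong sign for every patient whose baseline z is below 0, and unstable values near 0. That part is algebra. The size, about 28% to 97% of patients, rests wholly on assumed analyte values.

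Two stronger readings go too far. The first is that most patients are affected: this is true in three of the four scenarios but not in the fourth, and the documents cannot settle which applies. The second is that worsening fibrosis would be reported as improvement, or the trial's fibrosis result reversed. The correctly signed absolute change is listed alongside, Fibroscan and ELF are not shown to be affected, and the SAP does not state that a higher z means more fibrosis. The contradiction between the two columns holds whichever way z runs.

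Undefined values arise only if the log or geometric options are used, or at a baseline of exactly 0. The primary ALT analysis is untouched. This should be corrected before database lock.

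**What to change.** In SAP 6.2.2 and 6.2.3, exempt the fibrosis biomarker score z from percent change, ratio to baseline, log transformation and geometric mean/CV. State that it is analysed as absolute change from baseline with untransformed baseline as covariate.

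Alternatively, if a positive bounded form of the score is what will be reported, write that transformation into SAP 10.1.2 after z and apply the summaries to that form.

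In SAP 6.2.2, also omit percent change and geometric summaries for itch VAS. Its change-from-baseline analysis in SAP 6.2.3 stays as planned.

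The cost is a few lines of SAP text and edits to the table and listing shells. No new data are needed, and the only loss is columns that carry no usable meaning for these two variables.

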6.2.3 Statistical model, assumptions and hypotheses

Log-transformed ratio to baseline % liver fat and fasting lipid profiles as well as change from baseline % liver fat, weight, BMI, WTH ratio and itch VAS score will be analyzed. Parameters with more than one post-treatment measurement will be subjected to the same repeated measures ANCOVA described for the primary analysis using log-transformed baseline in lieu of untransformed baseline as a covariate for the log-transformed data analysis. For parameters with only one post-treatment measurement an ANCOVA with treatment as a classification factor and baseline (or log-transformed baseline if applicable) as a covariate will be employed.

Fibroscan® (in a subset of patients), ELF and fibrosis biomarker test data will be analyzed similarly and the log-transformation applied prior to the analysis as needed. For % liver fat, if historical placebo control data in a similar patient population are identified in the literature or become available from in-house studies later on then they may be incorporated into a Bayesian analysis as described for ALT.

The subgroup of subjects with baseline liver fat $\geq 10\%$ may be analyzed separately as needed.

Corporate Confidential Information

7 Statistical methods for safety and tolerability data

All subjects within the Safety analysis set will be included in the safety data analysis.

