6.3 Treatment assignment and randomization

Randomized treatment will be assigned to individual patients by way of a randomization number. Randomization numbers will be assigned in ascending, sequential order to eligible patients (see Site Operations Manual for details).

The randomization number is only used to identify which treatment the patient has been randomized to receive. The Patient number assigned to a patient at screening remains the unique identifier for the patient throughout the study. For information on patient numbering, please see ‘Patient numbering’ section in the Site Operations Manual.

The randomization numbers will be generated using the following procedure to ensure that treatment assignment is unbiased and concealed from patients and investigator staff. A patient randomization list will be produced by the IRT provider using a validated system that automates the random assignment of treatment arms to randomization numbers. These randomization numbers are linked to the different treatment arms.

Randomization will be stratified by BMI at baseline (<30 kg/m² or ≥ 30 kg/m² for patients with an Asian race, or <35 kg/m² or ≥ 35 kg/m² for all other patients). The race will be based on the race the patient self-reports as captured on the demography eCRF.

The randomization scheme for patients will be reviewed and approved by a member of the Randomization Office.

Follow the details outlined in the Site Operations Manual regarding the process and timing of treatment assignment and randomization of patients.

Table 6-1 provides general details of the numbering of patients for randomization into each cohort:

Table 6-1 Treatment Assignment Numbering – Cohort 1

Corporate Confidential Information	Race	BMI (kg/ m ²)	Randomization Numbers
	Asian	<30	5101-5292
	Asian	≥30	5301-5492
	Non-Asian	<35	5501-5692
	Non-Asian	≥35	5701-5892

Table 6-2 Treatment Assignment Numbering – Cohort 2Corporate Confidential
Information

Race	BMI (kg/ m ²)	Randomization Numbers
Asian	<30	9101-9292
Asian	≥30	9301-9492
Non-Asian	<35	9501-9692
Non-Asian	≥35	9701-9892

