8.5.2 Magnetic Resonance Imaging

Patients will undergo magnetic resonance imaging twice during the course of the study (Baseline and End of Treatment) to quantitate liver fat. Optional exploratory MRI based assessments will be performed in a subset of patients to evaluate the effect of LMB763 on other MRI related endpoints as outlined in [Section 8.1 \(Assessment schedule\)](#). All patients who discontinue prematurely must have an end of treatment MRI assessment.

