11.4.2 Statistical model, hypothesis, and method of analysis

A Bayesian approach will be used to analyze the change from baseline to Week 12 in ALT, which is assumed to follow a normal distribution with a known variance for each treatment arm. An informative prior for the placebo treatment effect and a non-informative prior for the LMB763 treatment effect will be incorporated into the analysis. The variance and the informative prior will be based on historical control data from studies such as the FLINT trial ([Neuschwander-Tetri et al 2015](#)). Median estimates, credible intervals and posterior probabilities that the placebo-adjusted ALT reduction by an LMB763 dose is (a) greater than 0 and (b) greater than 19 U/L and/or another cutoff value will be provided within the Bayesian framework. As a sensitivity analysis, the posterior probabilities will be calculated for varying values of the effective sample size for the placebo prior. A further sensitivity analysis using different values of the common variance assumed in the likelihood function and the prior may be performed as needed. An analysis using SAS PROC MCMC without assuming the variance is known in the likelihood function may be performed as well.

Additionally a repeated measures analysis of covariance (ANCOVA) will be performed for change from baseline ALT without using historical placebo control data. The model will include effects for treatment, visit, treatment by visit interaction, stratification factor (BMI group), baseline, and baseline by visit interaction. An unstructured variance-covariance structure will be used to account for correlation among multiple measurements from the same patient and variance heterogeneity. Point estimates, the associated two-sided 90% confidence intervals as well as the p-values for treatment differences will be obtained. The null hypothesis of no treatment difference will be tested at the one-sided 0.05 significance level. Both untransformed and log-transformed ALT will be analyzed. For log-transformed ALT analysis the ratio to baseline results obtained by back transformation will be reported

The cohort effect will be explored and a cohort-wise analysis for both the Bayesian and ANCOVA approaches may be performed as needed.

If placebo data from in-house studies in a similar patient population become available they may be included in an ANCOVA on log-transformed data via informative priors.

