 - Number and percentage of subjects with adverse events by system organ class
- Pharmacokinetic (PK) results for plasma:
 - Arithmetic mean (SD) concentration-time plot per treatment (overlying).
 - Summary statistics for PK parameters.
- Pharmacodynamic (PD) analyses include, but are not limited to:
 - Treatment response at Week 12 in ALT
 - Mean (SE) ALT plot per treatment (overlying) over time
 - Treatment comparison of key secondary parameters (Percent liver fat as measured by MRI, Weight, Fibroscan[®], ELF panel, fasting lipid profile and itch as assessed on the VAS scale) at Week 12

- Mean (SE) plots of key secondary parameters (Percent liver fat as measured by MRI, Weight, Fibroscan[®], ELF panel, fasting lipid profile and itch as assessed on the VAS scale) per treatment (overlying) and over time.

Corporate Confidential Information

4 Statistical methods: Analysis sets

For all analysis sets, subjects will be analyzed according to the study treatment(s) received. All placebo subjects will be pooled. Subjects with dose frequency/dose change due to AE will be analyzed according to the treatment they received up to the dose frequency/dose change.

All patients that received at least one dose of study drug will be included in the safety data analysis “safety population”.

The PK analysis set will include all subjects with at least one available valid (i.e., not flagged for exclusion) PK concentration measurement, who received any study drug and experienced no protocol deviations with relevant impact on PK data.

All patients with evaluable PD parameter data and no major protocol deviations impacting PD data will be included in the PD data analysis “PD population”.

For the End of Study (EOS) visit only data from study completers will be included in the summary/analysis tables/figures.

The data exclusion for each analysis set based on protocol deviation codes will be captured in the following table, which will be completed in a SAP amendment prior to DBL as needed.

Table 4-1 Protocol deviation codes and analysis sets

Category Deviation code	Text description of deviation	Data exclusion
	Subjects are excluded from all (safety) analysis in case of these protocol deviations:	Exclude subject completely from all (safety) analysis sets
	Subjects are excluded from PK analysis in case of these protocol deviations:	Exclude subject from PK analysis set

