6.1.3 Statistical model, assumptions and hypotheses

Bayesian approach

A Bayesian approach will be used to analyze the change from baseline to Week 12 in ALT, which is assumed to follow a normal distribution with a known variance for each treatment arm. An informative prior for the placebo treatment effect and a non-informative prior for the LMB763 treatment effect will be incorporated in the analysis. The variance and the informative prior will be based on historical control data from external and/or internal studies such as the FLINT trial (Neuschwander-Tetri et al 2015). Median estimates, 90% credible intervals and posterior probabilities that the placebo-adjusted ALT reduction by an LMB763 dose is (a) greater than 0 and (b) greater than 19 U/L and/or another cutoff value will be provided within the Bayesian framework.

The cohort effect will be explored and a cohort-wise analysis may be performed as needed.

If placebo data from in-house studies in a similar patient population become available they may be included in an ANCOVA on log-transformed data via informative priors.

Repeated measures approach

A repeated measures analysis of covariance (ANCOVA) will be performed for change from baseline ALT. The model will include effects for treatment, visit, treatment by visit interaction, stratification factor (BMI group), baseline, and baseline by visit interaction. The BMI group will have the following 2 strata: low BMI (Asian <30 and Non-Asian <35) and high BMI (Asian ≥ 30 and Non-Asian ≥ 35). An unstructured variance-covariance structure will be used to account for correlation among multiple measurements from the same patient and variance heterogeneity. If the unstructured covariance causes model convergence issues other simpler covariance structures will be considered. Point estimates, the associated two-sided 90% confidence interval as well as the p-values for treatment differences (including LMB 50 mg vs LMB 100 mg) will be obtained. The null hypothesis of no treatment difference will be tested at the one-sided 0.05 significance level. Both untransformed and log-transformed ALT will be analyzed, with log-transformed baseline in lieu of untransformed baseline as a covariate when log-transformed ALT is analyzed. For log-transformed ALT analysis the ratio to baseline results obtained by back transformation will be reported.

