Additionally a repeated measures ANCOVA treating all post dose adjustment measurements as missing will be performed as well if the number of patients with dose adjustment is not small (for example, >20%).

The cohort effect will be explored and a cohort-wise analysis may be performed as needed.

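### The ANCOVA that applies to % liver fat leaves out the BMI-group stratification factor that the repeated-measures model keeps

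*SAP*

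**What the plan says.** Protocol 6.3: "Randomization will be stratified by BMI at baseline", with cut-offs that depend on race. Tables 6-1 and 6-2 give each cohort its own blocks of randomisation numbers.

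SAP 6.1.3, for the repeated-measures ANCOVA: "The model will include effects for treatment, visit, treatment by visit interaction, stratification factor (BMI group), baseline, and baseline by visit interaction". It defines BMI group as two levels, low and high. Protocol 11.4.2 lists the same terms.

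Protocol 8.5.2: "Patients will undergo magnetic resonance imaging twice during the course of the study (Baseline and End of Treatment) to quantitate liver fat". Liver fat therefore has a single value after baseline.

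SAP 6.2.3, for such variables: "For parameters with only one post-treatment measurement an ANCOVA with treatment as a classification factor and baseline" (log-transformed where applicable) as covariate. Protocol 11.5.1 has the same sentence. It first lists liver fat among the variables for the repeated-measures model and then gives this separate rule. The SAP makes the split explicit.

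SAP Section 4 (analysis sets): "All placebo subjects will be pooled".

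**The concern.** When randomisation is stratified, the analysis model normally carries the stratification factor. The restricted allocation removes chance imbalance in that factor, and a model without it does not credit the gain: its residual variance still contains the between-stratum variation, so the standard error is somewhat too large. This plan follows the convention for ALT and for every other variable in the repeated-measures model. It departs from it, without explanation, for variables measured once after baseline. Liver fat is the visible case. It has its own power statement (protocol 11.8) and is among the key secondary results in SAP Section 2.

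There is a second, weaker reason to want the term. Stratification balances BMI group between arms within a cohort. Each dose will be compared with placebo patients from both cohorts, and the separate lists do not guarantee balance in that comparison.

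At stake are a little precision and consistency between models.

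**Working it through.** **Inputs from protocol 11.8:** SD 4.02 points; 54 treated and 27 placebo completers per cohort; one-sided 0.05; differences of 1.64 and 2.46 points.

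**Assumed, because the documents give no figure:** R2, the share of variance in liver-fat change that BMI group explains after baseline, taken as 0 to 10%. The SD of 4.02 is treated as the residual SD after baseline, and the two strata as equal in size.

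**Step 1: the plan's own figure.** SE = 4.02 × sqrt(1/54 + 1/27) = 0.948. Noncentral t power with 79 df is 52.8% at 1.64 and 82.4% at 2.46, against the stated 52% and 82%. It reproduces, and the calculation contains no stratum term.

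**Step 2: the pooled comparison.** Placebo from both cohorts gives 27 + 27 = 54. SE = 4.02 × sqrt(2/54) = 0.774.

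**Step 3: what each R2 means.** With two equal strata whose means differ by g, the between-stratum variance is (g/2)². Setting this equal to R2 × 4.02² gives g = 2 × 4.02 × sqrt(R2).

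**Step 4: formulas (normal approximation, strata balanced between arms, true difference d).**
- Term omitted, type I error: 1 − Φ(1.645 / sqrt(1 − R2))
- Term omitted, power: Φ((d/SE − 1.645) / sqrt(1 − R2))
- Term included, power: Φ(d / (SE × sqrt(1 − R2)) − 1.645)

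Example at R2 = 5%: sqrt(0.95) = 0.975 and 1.64/0.774 = 2.120. Type I error is 1 − Φ(1.688) = 4.6%. Power without the term is Φ(0.487) = 68.7%; with it, Φ(0.530) = 70.2%.

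| Assumed R2 | Stratum gap g (points) | Type I error without term | Power at 1.64 without / with | Gain at 1.64 | Gain at 2.46 |
|---|---|---|---|---|---|
| 0% | 0 | 5.0% | 68.3 / 68.3% | 0 | 0 |
| 1% | 0.8 | 4.9% | 68.3 / 68.6% | 0.3 | 0.1 |
| 2% | 1.1 | 4.8% | 68.4 / 69.0% | 0.6 | 0.2 |
| 5% | 1.8 | 4.6% | 68.7 / 70.2% | 1.5 | 0.5 |
| 10% | 2.5 | 4.1% | 69.2 / 72.2% | 3.1 | 0.9 |

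Gains are in percentage points, from unrounded values.

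**Step 5: BMI mix differing between cohorts.** Let the share of high-BMI patients differ by m. Pooled placebo, with 27 from each cohort, sits midway, so each dose arm differs from it by m/2. The bias is (m/2) × g = 4.02 × sqrt(R2) × m, in opposite directions for the two doses. For an assumed m of 0.10 it is 0.04, 0.06, 0.09 and 0.13 points at R2 of 1, 2, 5 and 10%. Shifting the type I formula by bias/SE gives 5.5% for one dose and 4.4% for the other at R2 of 1%, and 5.6% and 4.1% at 2%.

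**The case against.** **Both documents prespecify the same model, and it is valid.** True. Adjusting for baseline alone is legitimate in a randomised comparison, the study is non-confirmatory, and liver fat is secondary. This limits the point to consistency and precision.

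**The larger R2 values are demanding.** True. R2 of 5% and 10% imply that the BMI groups differ by 1.8 and 2.5 points after baseline adjustment. Both exceed the 1.64-point planning difference, and the second also exceeds 2.46. At 1 to 2% the gain is only 0.3 to 0.6 points of power.

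**There is no documented reason for the BMI mix to differ between cohorts.** True. The BMI entry criteria in protocol 4.1 are identical. The cohorts differ in the ALT cut-off and in the 10% liver-fat requirement, and baseline liver fat is already in the model. A reader might infer from the pooling that the liver-fat comparison is biased or its type I error inflated. The documents support only the possibility of a small bias if recruitment or chance produced a different mix. The BMI term would remove only the part that runs through the two-level factor.

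**Cohort differences of other kinds.** A reader might also infer that a cohort effect on liver fat goes unexamined. That is a separate question, which the BMI term would not answer, and the text does not establish it. Protocol 11.5.1 refers liver fat to Section 11.4.2, which says "The cohort effect will be explored and a cohort-wise analysis for both the Bayesian and ANCOVA approaches may be performed as needed", and text after SAP 6.2.3 is redacted.

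Redaction does not explain the missing term itself. The model sentence is complete in both documents, and protocol 11.5.1 shows no redaction.

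**Conclusion.** The point holds as a minor inconsistency that is almost free to correct. The model for liver fat drops a factor that stratifies the randomisation and that the companion model includes, and no reason is given.

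A reader might infer that the stated liver-fat power is wrong. It is not: it reproduces, and it never assumed a stratum term. Within a cohort there is no bias, and with balanced strata the one-sided error stays at or below 5% (4.1% at the lowest in the table). The gain from adding the term lies between nothing and about 3 points of power at a 1.64-point difference, and is under 1 point at 2.46. The upper end requires a BMI-group effect larger than the treatment effects used for planning.

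These sizes rest on the assumed R2, equal and balanced strata, and 4.02 as the residual SD. The true effect may be zero.

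**What to change.** In the single-measurement sentence of SAP 6.2.3 and protocol 11.5.1, insert *and BMI group (two levels, as in SAP Section 6.1.3)* after the word treatment, and make the classification factor plural. Leave the baseline covariate, the pooled placebo group and the ALT model as they are. If the omission was deliberate, state the reason instead.

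The cost is one degree of freedom, using a factor already collected. In the 54 versus 27 comparison with no BMI effect, moving from 79 to 78 df leaves t-based power at 1.64 points at 52.8%.

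The rule covers every variable with one post-treatment value. If a variable collected only in a subset falls under it, check before fitting that both BMI strata are populated.
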